### 10.2.4 Detection of Adverse Events Following Immunization (AEFIs)

Although routine pharmacovigilance is not conducted as part of the research protocol, the routine pharmacovigilance system will be strengthened through a standardised set of activities to support staff at all health facilities located within the MVIP areas (section 7.6). This pharmacovigilance strengthening will be the responsibility of the health care system, as will routine reporting on AEFI and AESI (see also section 13.2) with support from WHO. The strengthened pharmacovigilance system is designed to capture any spontaneously reported vaccine-related adverse events, including febrile convulsions and rare and unexpected AEFI, which might be experienced by some children following RTS,S/AS01 vaccination.

Adverse Events of Special Interest (AESI) may be captured through country-specific protocols, as agreed with national authorities, as a complement to the detailed information generated by GSK’s Phase 4 study.

### 10.3 Study procedures

Data from all children admitted to hospital should be captured in a routine health Management Information System (HMIS). This will typically include minimal demographic and clinical information such as name, age, gender, area of residence, diagnosis, treatment and outcome (dead, alive, referred). Some hospitals may have an electronic system but the majority are expected to be paper-based. The content and functioning of the HMIS will be reviewed before study start and arrangements made to augment data collection, as necessary, for children in the target age range (i.e. from 1 month - 4 years inclusive). Informed consent will be sought for capture of any data not routinely collected and according to local requirements.

Demographic information, RTS,S/AS01 and other vaccination status, key clinical signs - including criteria for lumbar puncture - details of samples collected and the result of malaria and CSF testing will be captured in a CRF, as appropriate. An algorithm for investigations will be developed that is consistent with national guidelines, with agreed criteria in each country for sample collection. Relevant clinical staff will be provided with refresher training on the relevant national routine care guidelines to facilitate patient management according to the national guidelines. The MoH in each country will retain responsibility for assuring the availability of the treatments it recommends in its national guidelines. At the same time, the staff will also be trained in the pilot programme's investigation algorithm (which is aligned with the WHO and national guidelines of the three pilot countries) to ensure that children are assessed in a standard way, with blood and CSF samples collected as necessary to enable assessment of study endpoints against standardised case definitions. The MVIP will work with the MoH and evaluation partners to assure, as far as possible, the availability of the supplies needed for essential investigations and treatment.

Children will be managed according to national guidelines and the final clinical diagnosis and outcome will be recorded at the end of admission. All relevant clinical and laboratory data will be compiled in an electronic CRF to enable case ascertainment for the analysis of the evaluation's endpoints.

The enhanced hospital-based surveillance will be in place prior to the introduction of RTS,S/AS01, generating data for Programme Advisory Group review to confirm the integrity of the surveillance and allowing an assessment of the comparability of facilities in implementing and comparison areas in terms of completeness and quality of the data. Data from the enhanced HMIS will be monitored until the end of the evaluation, approximately 50 months after the start of vaccination (see section 9.2.1), using automated data routines to evaluate completeness and internal consistency of records.

Children with any sequelae following a diagnosis of meningitis or cerebral malaria will be invited to re-attend hospital for follow-up appointments after hospital discharge. These will be scheduled at intervals considered appropriate by the attending clinician.

If, at any time, the attending clinician suspects the admission is related to RTS,S/AS01 the procedures to report an AEFI should be followed (see section 13) and the Evaluation Partner's Clinical Surveillance Coordinator notified by phone or SMS text message. The fact that an event was reported as an AEFI will be captured in the CRF.

### 10.3.1 Data capture in sentinel hospitals

Children will be admitted to hospital according to local procedures. At the time of admission the standard HMIS data will be documented according to standard practice. All children aged 1 to 59 months will have a brief purpose-made questionnaire completed by the attending clinical staff in order to capture the demographic, vaccination and clinical information necessary to trigger specific investigations and eventually enable a final diagnosis to be made. Completeness of the hospital surveillance will be checked during the daily ward rounds, at which time every admission in the target age group should have had a hospital surveillance screening form completed, and at period visits by the clinical surveillance co-ordinator of the in-country evaluation partners. Completeness of data capture in the enhanced HMIS will be assessed through triangulation with hospital admission registers. Hospital staff will be encouraged to contact the clinical surveillance co-ordinator by phone in case of any concern or uncertainty regarding the assessment of patients contributing to the evaluation.

### 10.3.2 Informed consent for the collection of surveillance data

Where considered necessary by local IRBs, written, or witnessed and thumb-printed, informed consent will be obtained from each child's carer before data are included in the evaluation dataset. The intention is to capture data that should in any case be documented as part of clinical care. Consent will be sought for any data capture, diagnostic procedure or test required by the study which would not otherwise be needed to satisfy the relevant national paediatric inpatient protocol. Country-specific protocols will address this point in detail and provide country-specific information. The seeking of consent and capture of any study-specific data should not impede the assessment or management of the child. Data may be captured retrospectively once the Informed Consent Form (ICF) is signed/ thumbprinted. No study-specific procedures, including any follow-up visits specially-scheduled for the purposes of the evaluation, will be performed before the ICF is signed/ thumbprinted.

### 10.3.3 Data to be captured

The following data will be collected into a CRF (paper or electronic, annex 12) from all children aged 1-59 months admitted to hospital:

- From the standard, routine HMIS: age, date of admission, gender, normal place of residence (village or urban address), current place of residence if this is different, diagnosis, treatment and outcome of admission. Records will include identifiers of the sentinel hospital and the patient's hospital number.

Children from the programme area will have the following additional information collected:

- Date of birth (if not included in the routine HMIS), active participation in any clinical trial.
- Use of malaria control measures (ITN, IRS, anti-malaria drugs), other health care seeking for the current illness or drug use in the previous 14 days. This will include whether evidence of prescription was available or if drug use was reported, and capture information on antibiotic and anti-malarial use (which may affect detection of bacteria and/or *P falciparum*), and medication for chronic conditions (e.g. HIV).

- Vaccination history – types and dates of vaccinations received through the routine EPI. This will be captured from the child’s health card wherever possible. A photograph of the health card may be taken and stored with the child’s CRF to facilitate validation of vaccinations and dates. This will include dates of vaccination with OPV, BCG, DTP (or DTP/HepB/Hib, as appropriate), measles and RTS,S/AS01. Where no health card is available the information will be solicited from the caregiver through verbal recall (no dates) and documented as such. When vaccination information is collected through maternal recall, the caregiver/mother will be asked about each vaccine (per country-specific EPI guidelines) and the number of doses, with detailed prompts characterizing the vaccines to enhance the quality of the recall (e.g., describing oral polio vaccine as bitter drops; etc.). In a subset of cases, parents may be asked additional questions to validate maternal recall . Where a vaccine record or maternal recall do not provide information on the vaccine status, the potential to seek information from the clinic registers for meningitis and cerebral malaria cases in vaccine-eligible age groups in RTSS clusters will be considered where feasible.
- Any known pre-existing medical conditions e.g. HIV infection, congenital disease (including haemoglobinopathies).
- History of fever, difficulty breathing, convulsions, altered consciousness.
- Findings from physical examination including body temperature, respiratory rate, presence of chest indrawing, deep breathing, the components of the Blantyre Coma Score, neck stiffness, bulging fontanelle.
- Whether a blood sample was collected and, if so, the tests requested, results available during the admission and sample identification number for tests requested off the paediatric ward. All children will be expected to have a malaria test (RDT and microscopy) and a haemoglobin/PCV.

In addition, children under 2 years of age with a BCS <3, or assessed as P or U on AVPU score, or aged 2 years and over and with a Glasgow Coma Score <11, will have the following data captured:

- Blood glucose result
- Whether a CSF sample was collected and, if so, the sample identification number and results available during admission.

At the time of discharge a final main and any secondary diagnoses will be recorded by the attending clinician, taking into account the clinical assessments, available test results, evolution of the illness and response to treatment, and the final outcome (alive, dead, referred, absconded).

All data will be recorded in a record form (CRF) and entered into the programme’s database.

---

 AVPU: Alert, responding to Voice, responding to Pain, Unresponsive

### 10.3.4 Sample collection

Details of suspected meningitis or cerebral malaria cases – including medication history, findings on clinical examination and results of diagnostic testing - will be recorded in the CRF. Part of the CSF sample, collected according to routine practice, will be stored for further testing at the reference laboratory. Standard Operating Procedures will be implemented to govern sample storage and the transfer of samples to the central laboratory.

Local analyses of blood & CSF samples will be undertaken on site to the extent possible (table 5) and samples stored for additional processing in a reference laboratory. In some cases, anti-CS or anti-Hep B antibodies may be measured as supportive evidence of prior RTS,S/AS01 vaccination. Details of which examinations will be performed in which hospitals will be confirmed only once the hospitals have been selected but are expected to fall into the categories in table 5. At a minimum, CSF examination will include visual inspection before freezing and shipment to reference laboratories. Some hospitals may, in addition, perform microscopy, glucose and protein measurement, and run antigen detection tests, and a few will also culture CSF samples.

### 10.3.5 Record review

The clinical surveillance co-ordinator in each country will review clinical data as it accumulates to ensure its accuracy, completeness – including availability of sample information and local laboratory results - and internal consistency. Data monitoring at hospital, evaluation partner, country and programme levels will be supported by automated data review routines to enable targeted case review and follow-up action.

## 10.4 Case definitions

### 10.4.1 Meningitis

Meningitis was identified as a potential risk during the RTS,S/AS01 phase 3 study and particular efforts will be made to identify meningitis cases, defined in line with WHO's meningitis surveillance guidelines. For all cases with a diagnosis of meningitis, and a sample of non-meningitis diagnoses, an independent expert review, blinded to vaccine status, may be conducted on the patient's record (this is dependent on the ability to conduct a record review beyond the CRF) before a final diagnosis is provided. This is required to manage, in a standardised way across the MVPE, the potential confusion between meningitis and other severe illnesses, such as cerebral malaria.

Table 6 summarises the meningitis case definitions. **“Suspected meningitis”** is a diagnosis based on clinical symptoms and/or signs defined as:

*A child with one or more of the following present (with or without fever , neck stiffness, two or more seizures in the last 24 hours, bulging fontanelle, convulsions (partial, complex febrile or other atypical presentations), seizures if less than 6 months or greater than 6 years , altered consciousness, (Blantyre Coma Score less than 3 or, Glasgow Coma Score less than 11 or P or U on the AVPU scale [Alert Verbal Painful Unresponsiveness Scale]) or any other clinical symptoms indicative of meningitis or cerebral malaria by clinical judgement. Lumbar puncture will be encouraged in all such children, according to national diagnostic and treatment guidelines, for examination of cerebrospinal fluid (CSF).*

Children will be considered to have “**probable meningitis**” if:

*In a suspected case, the macroscopic aspect of the CSF is turbid, cloudy or purulent; or the CSF leukocyte count is >10 cells/mm^3.*

A child will be classified as a “**confirmed meningitis**” case if:

*A suspected or probable case is laboratory confirmed by culturing or identifying (i.e. by polymerase chain reaction) bacterial, viral or other aetiology in the CSF.*

Table 6: Meningitis case definitions for the MVPE

Clinical signs & laboratory results	In-country meningitis category	Results from Reference lab	Final meningitis category for analysis
[No neck stiffness AND (No altered consciousness OR alternative explanation for altered consciousness) AND No other meningeal sign*]	Not a meningitis case	Not needed for definition	Not a meningitis case
If one or more of the following is present (with or without fever): neck stiffness, two or more seizures in the last 24 hours or another meningeal sign including bulging fontanelle, or any seizures if less than 6 months, altered consciousness, (Blantyre Coma Score less than 3 or, Glasgow Coma Score less than 11 or P or U on the AVPU scale [ Alert Verbal Painful Unresponsiveness Scale]) or any other clinical symptoms indicative of meningitis or cerebral malaria by clinical judgement	Suspected meningitis	Not needed for definition	Suspected meningitis
Any suspected case with macroscopically turbid, cloudy or purulent CSF; or with a CSF leukocyte count >10 cells/mm^3.	Probable meningitis	No aetiological agent found or no sample available	Probable meningitis
Any suspected or probable case that is laboratory confirmed by culturing or identifying (i.e. by polymerase chain reaction) of bacterial, viral or other aetiology in the CSF .	Bacterial or viral meningitis	No aetiological agent found or no sample available	Probable meningitis
		Aetiological agent identified	Aetiology confirmed meningitis

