#### 10.4.2 Malaria

WHO's case definitions for malaria will be used. For all cases of severe malaria, including cerebral malaria, an independent expert review, blinded to vaccine status, may be conducted on the patient's record before a final diagnosis is provided (this is dependent on the ability to conduct a record review beyond the CRF). This is required to manage, in a standardised way across the MVPE, the difficulties of making some diagnoses, particularly cerebral malaria, which are difficult to standardize *a priori*.

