## 10.9 Case ascertainment

An algorithm will be developed to categorise the meningitis and cerebral malaria status of all age-eligible admissions to sentinel hospitals, according to the case definitions presented in section 10.4. The in-country evaluation partners will run the algorithm on the data for which they are responsible and assess the consistency of the algorithm-based diagnosis with the clinical diagnosis made in the light of the clinical history, signs on examination, results of investigations and response to treatment. If the case is classified as an AEFI, these data and classifications will be submitted to the National AEFI Review Committee (ARC) for review and validation. No assessment of causality will be made at the individual level for meningitis or cerebral malaria. Rather, conclusions about the likelihood that RTS,S/AS01 is responsible for a change in meningitis or cerebral malaria rates will be based on the analysis of data on exposure to the vaccine in the implementation and comparison areas.

The ARC will verify and classify all AEFI reported through the routine system before presentation to the cross-country Data Safety Monitoring Board (DSMB). During the DSMB meetings, the data will be presented from the three countries on the AEFI findings and on the MVPE safety analysis.

The DSMB will be provided the ARC assessments of the initially unclassified cases and have access to experts in meningitis and severe malaria diagnosis to inform their final decision on the classification, for analytical purposes, of individual cases. The experts may be provided with all available medical information on individual cases but will initially be agnostic to vaccine exposure.

Both the ARCs and DSMB will operate according to agreed terms of reference and adhere strictly to the protocol-defined case definitions. Each will make causality assessments for adverse events reported through routine pharmacovigilance; those of the DSMB will be considered definitive for the purposes of the analysis across the three countries of the MVIP.

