In each RTS,S cluster, children under 5 years of age can be classified into those eligible to receive RTS,S and those who are not eligible either because they are too young or there were too old when RTS,S vaccination started. Classification into eligible (group A) and non-eligible (group B) is based on date of birth and age, not on whether they actually received RTS,S, so the classification can be applied in exactly the same way in both intervention and comparator clusters (Figure 2):

[figure not shown]
Figure 2. Classification of age-eligible and non-eligible children in the RTS,S vaccination and comparator areas (Malawi example).

Assuming introduction of RTS,S has no influence on incidence in non-eligible children, the difference in incidence between group B in the RTS,S arm and group B in the comparator area, reflects differences unrelated to RTS,S (such as differences in access to hospital, differences in underlying rates, or differences in diagnostic performance of hospitals or, for deaths, differences in the completeness of mortality surveillance). The difference in incidence between group A in the RTS,S arm and group A in the comparator arm, reflects these same differences *and* the effects of the introduction of RTS,S. We would like to subtract the Group B differences from the Group A

differences to get a better estimate of the effect of RTS,S introduction. Equivalently, we can consider the difference between Group A and Group B in the comparator area, and subtract this from the difference between Group A and Group B in the RTS,S arm (Figure 3); this way round is advantageous because the initial differencing is done within each cluster, thus eliminating the differences between the clusters in baseline incidence, access to hospital and diagnostic performance of the hospital etc. The test to assess the effect of RTS,S introduction amounts to a test for interaction between vaccine arm and group (A or B), [6,7 (p272-4)].

Figure 3: Comparison of between implementation and comparator areas, of the within-cluster differences.

The same approach can be used to determine if the effect of RTS,S on mortality differs between girls and boys. The mortality rate ratio between girls and boys (who are eligible for vaccination) in clusters in the RTS,S arm, is compared with the mortality rate ratio between eligible girls and boys in clusters in the comparator area.

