13. Completeness of surveillance

Completeness of surveillance will be monitored during the project and will be reported at each analysis time point. Indicators of completeness are,

For mortality:

- the number of weekly reports per village or per reporter, tabulated per month per cluster in each arm
- in each area of the evaluation: the number of deaths reported, and the number of these with VA completed, and the time interval between death and VA, by cluster and eligibility group and by gender

For meningitis:

- for each hospital in each month, the number of patients admitted in the target age range, the number eligible for lumbar puncture, and the number who had lumbar puncture performed with CSF results, tabulated by gender and vaccine eligibility group.

For all types of event, overall and by cluster and by eligibility-group:

- % events with missing information on age, address, vaccine status
- % events with incomplete information on age, address, vaccine status
- % events with vaccine status by HBR, % by recall only, % missing
- % of children whose details were reported by the primary caregiver and the % reported by a proxy for the caregiver
- Check for duplicated events: number of events of each type with the same location, gender, age and date.

As a check on completeness of mortality surveillance, midline household surveys may include questions about under 5 deaths in the last year, and check to see if those deaths were captured by the surveillance system.

14. Laboratory quality control

For meningitis, CSF samples will be sent to ...for identification of causative organism by PCR. (Note that there is likely to be a delay, samples to be sent in shipments quarterly and analysis likely to take 4-6 weeks. However, confirmed meningitis is not a primary outcome).

15. Vaccination status

Indicators of data quality

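### Expert review of meningitis and malaria cases is masked to vaccine status but not, as written, to area, and lumbar puncture uptake is never tabulated by arm and eligibility together

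*Protocol*

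**What the plan says.** **Review.** Protocol 10.4.1 says of meningitis diagnoses that "an independent expert review, blinded to vaccine status, may be conducted", and 10.4.2 (severe and cerebral malaria) uses the same terms: "an independent expert review, blinded to vaccine status, may be conducted on the patient's record before a final diagnosis is provided". The review is optional and depends on access to records beyond the CRF, although both sections go on to call it required. For the experts who advise the DSMB, Protocol 10.9 says: "The experts may be provided with all available medical information on individual cases but will initially be agnostic to vaccine exposure". None of these sections mentions residence, cluster or arm.

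**Exposure analysed.** Protocol 10.12 and SAP section 6 compare areas within age groups. "Classification into eligible (group A) and non-eligible (group B) is based on date of birth and age, not on whether they actually received RTS,S".

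**Ward ascertainment.** Under Protocol 10.3.1, attending staff complete a form to "capture the demographic, vaccination and clinical information necessary to trigger specific investigations and eventually enable a final diagnosis to be made". Annex 12 has a field for implementing or comparator residence on the same form, ahead of the LP prompts, and Protocol 7.6.2 makes the allocation public. Suspected meningitis (10.4.1) can rest on clinical judgement. The protocol's cerebral malaria definition (10.4.2) requires both a clinician's diagnosis and an LP.

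**Monitoring.** Protocol 10.13 follows, by hospital and by area, the number needing LP and the number with a CSF result. SAP section 13 reports, for each hospital and month, "the number eligible for lumbar puncture, and the number who had lumbar puncture performed with CSF results, tabulated by gender and vaccine eligibility group".

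**The concern.** A mask protects a comparison only if it hides the variable being compared. Here the compared variable is area of residence crossed with age-eligibility. A reviewer who sees residence and age can place the child in the analysis table without knowing the vaccination record, and is also close to knowing that record.

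The same knowledge is available earlier, on the ward, and there it cannot be removed: delivery is routine and public, and carers are asked to bring the vaccination card. Probable meningitis, the protocol's cerebral malaria and the SAP's stricter cerebral malaria all need an LP, so the decision to do one determines whether a case can exist. Staff may know of the phase 3 signals. If they investigate eligible or vaccinated children in implementation areas more readily, or less readily, the eligible count changes in one arm only and the result reads as a vaccine effect, or hides one. These are primary safety outcomes, so it should be possible to see from the reported data whether this happened.

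**Working it through.** **Inputs.** RTS,S dose 1 coverage is 74% in implementation areas (73.7% in SAP Table 4) and 4% in comparator areas (SAP Table 5 notes). Target ratios are 5.66 for meningitis and 2.03 for cerebral malaria (SAP Table 5). The documents give no LP uptake and no size for differential investigation, so those values below are assumptions.

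**Check on the inputs.** The dilution formula is R = (c·Rv + 1 − c)/(d·Rv + 1 − d), with c = 0.737 and d = 0.04.
- Meningitis, Rv = 10.5: 0.737 × 10.5 + 0.263 = 8.00; divided by 1.38 gives 5.80. Table 5 states 8.00 and 5.80, before its confounding step to 5.66.
- Cerebral malaria, Rv = 2.57: 0.737 × 2.57 + 0.263 = 2.16; divided by 1.063 gives 2.03. Table 5 states 2.16 and 2.03.

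**What area reveals.** Knowing the area of an eligible child moves the chance of having had dose 1 from 4% to 74%, a ratio of 0.74/0.04 = 18.5.

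**What cancels.** Take no vaccine effect and let q be relative ascertainment. The SAP estimate is (eligible/non-eligible in RTS,S areas) ÷ (the same in comparator areas).
- q applies to all ages in implementation areas: (q/q)/(1/1) = 1.00.
- q applies only to eligible children in implementation areas: the spurious ratio is q.
- q follows recorded vaccination: (0.74q + 0.26)/(0.04q + 0.96), which is 1.17 at q = 1.25 and 1.34 at q = 1.5.

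**In terms of LP uptake.** Let u be uptake among suspected cases and δ the difference in known recipients, with equal CSF positivity in the extra LPs. The spurious ratio is (u + 0.74δ)/(u + 0.04δ).

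| u | δ | Calculation | Spurious ratio |
|---|---|---|---|
| 0.6 | 0.1 | 0.674/0.604 | 1.12 |
| 0.6 | 0.2 | 0.748/0.608 | 1.23 |
| 0.8 | 0.1 | 0.874/0.804 | 1.09 |

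**What it would take to create the targets.** Solving the vaccination-following formula for q gives q = (0.96t − 0.26)/(0.74 − 0.04t).
- t = 2.03: 1.689/0.659 = 2.6.
- t = 5.66: 5.174/0.514 = 10.1.

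**Opposite direction.** If eligible children in implementation areas are investigated less (q = 0.8), a true 2.03 becomes 0.8 × 2.03 = 1.62 and a true 5.66 becomes 4.53.

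**Where the bias would show.** Protocol 10.13 gives LP figures by hospital and area; SAP section 13 gives them by hospital and eligibility group. A hospital does not stand in for an arm, because Protocol 10.2.1 allows one hospital to serve both kinds of cluster. The indicators that SAP section 13 reports by cluster and eligibility group cover missing data and the source of vaccine status, not LP. The checks listed in SAP section 8 for a suspected safety excess do not mention LP uptake.

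**The case against.** A reader might infer that both hospital safety outcomes are assessed unmasked. The documents do not support that. Probable meningitis rests on CSF appearance or a leukocyte count above 10. The SAP's cerebral malaria definitions (Table 3) use a malaria test, a coma score and CSF findings, with no clinician diagnosis. An algorithm categorises all age-eligible admissions (Protocol 10.9), and any review is masked to the child's own vaccination. That reviewers will see area is an inference from silence: country protocols and the committees' terms of reference may say more. This stands, with one limit: a CSF rule is objective only once the LP has been done.

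Nor is masking vaccine status pointless. Case vaccination status is itself analysed (SAP sections 8 and 15).

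The arithmetic describes LP decisions on the ward. Reviewers see the record afterwards and cannot create an LP, so the gap in the review mask carries no number here. The uptake values are assumed, and if the extra LPs have a lower yield the bias is smaller. The SAP's broader cerebral malaria definition needs no LP; extra LPs can only remove cases from it, so the illustration does not apply there.

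Safeguards exist: most LP prompts in Annex 12 are sign-based, a reason is recorded when an indicated LP is not done, and area-wide differences in diagnosis cancel. They narrow the problem without covering ascertainment that differs by eligibility or vaccination within one arm.

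Moving the vaccination section of the form behind the LP fields might look like a remedy. It would leave residence and age ahead of the LP decision, so it is not proposed.

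**Conclusion.** The point holds in a limited form. The optional expert review is masked, as written, to vaccine status only, while the primary safety contrast is area by age-eligibility. Ward ascertainment is necessarily open. Ascertainment that differs for eligible or vaccinated children in implementation areas does not cancel, and no planned table would show it by arm.

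The illustrative bias, 1.09 to 1.23, rests on assumed LP uptake of 60–80%, a 10–20 point difference in known recipients, and equal CSF positivity. It could not plausibly produce a meningitis ratio near 5.66, which would need about tenfold ascertainment. It matters more for LP-required cerebral malaria, where the target is 2.03, and there it could weaken a real signal as well as inflate a null one. This is a cheap improvement, not a defect that undermines the design.

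**What to change.** 1. In Protocol 10.4.1 and 10.4.2, and for the DSMB's experts in 10.9, replace masking to vaccine status or exposure alone with: *blinded to vaccination history, residence, cluster and arm, and to hospital where it identifies the arm*. Redact those fields from the review file.

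2. In SAP section 13, tabulate the number eligible for LP and the number with LP and CSF results by arm × eligibility group. Add that table to the bias checks that SAP section 8 lists for a suspected safety excess.

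The cost is redaction work and one more dimension in a table built from data already collected. Neither change alters which children are offered an LP.
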